**Research on the Association Between the Inclination of the
Proximal Tibiofibular Joint Surface and Medial Compartment
Knee Osteoarthritis**

ClinicalTrials.gov ID: NCT03147495

2017.2.10

Study Protocol

Study Design and Patient Selection

This case-control study (Level III Evidence) will be performed in line with the principles of the Declaration of Helsinki.

The study will be performed to compare the inclination angle of the PTFJ surface in participants with and without medial compartment knee osteoarthritis. A sample size power analysis was conducted before the study, which revealed that a minimum of 39 subjects per group was needed to achieve statistical significance with two-sided $\alpha=0.05$ and $1-\beta=0.80$ and an assumed mean difference between two groups=65% of the standard deviation. The participants will be enrolled at the outpatient clinic of our hospital. The patients with medial compartment knee osteoarthritis will be enrolled at first. The anticipated number of patients is 40, and the female-to-male ratio is expected to be 1:1. Then, the participants of the control group will be enrolled and matched for sex and age (within 5 years) to the patients. The control-to-patient ratio is expected to be 1:1.

Inclusion criteria for participants of the patient group will be: (1) minimum age of 50 years, (2) symptomatic knee osteoarthritis according to the American College of Rheumatology criteria for the classification and reporting of osteoarthritis of the knee joint, (3) predominance of self-reported pain over the medial aspect of the knee, (4) radiographic evidence of medial compartment knee osteoarthritis with an Ahlbäck score of grade I or greater, and (5) radiographic evidence of lateral compartment with Ahlbäck classification grade 0. We will exclude participants with any previous

surgery, severe trauma, inflammatory joint disease, or tumors in the affected limb.

Our controls will be participants aged 50 years or older, without knee osteoarthritis according to the American College of Rheumatology criteria for the classification and reporting of osteoarthritis of the knee joint, and with radiographic evidence of the knee with Ahlbäck classification grade 0. Exclusion criteria will be a history of previous surgery, severe trauma, inflammatory joint disease, or tumors in the affected limb.

All participants should give signed informed consent before enrolment.

Radiographic Examination

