be assessed with the two-sample t test. Furthermore, the participants of each group will be separately grouped into sex subgroups and into two age subgroups. The old age subgroup of each group will include approximately 20 participants with earlier ages, and the remaining participants with higher ages will form the older age subgroups (The number of participants in each subgroup will be as close as possible to 20). The two-sample t tests will be repeated for each sex subgroup and age subgroup in isolation. The odds ratios (ORs) for risk factors of medial compartment knee osteoarthritis will also be calculated by using binary logistic regression analysis.

The PTFJ types will be compared between the two groups by using the χ^2 test. The PTFJ osteoarthritis grades will be compared between the two groups by using the Mann-Whitney U test.

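### Controls are matched to patients on sex and age, but the between-group analyses neither use the matching nor name sex and age as covariates

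*Combined protocol and SAP*

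**What the plan says.** Under Study Design and Patient Selection, patients are enrolled first. On the controls, the plan says "the participants of the control group will be enrolled and matched for sex and age (within 5 years) to the patients". One control per patient is foreseen, with 40 patients anticipated. This reads most naturally as individual matching, but the plan does not say so and mentions no pair identifier.

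Under Statistical Analysis Plan, differences in the fibular inclination angle (FIA) and tibial inclination angle (TIA) between patients and controls will "be assessed with the two-sample t test". For subgroups, "the participants of each group will be separately grouped into sex subgroups and into two age subgroups", and the same test is repeated in each. ORs for risk factors "will also be calculated by using binary logistic regression analysis", with no covariates listed. "The PTFJ types will be compared between the two groups by using the χ^2 test", and joint osteoarthritis grades are compared with the Mann-Whitney U test. The only paired test compares FIA with TIA across all participants, not patient with matched control.

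**The concern.** Matching makes the two groups alike in sex and age. If the angles depend on those factors, the difference in means then varies less from study to study than two independent samples would suggest. The two-sample standard error does not reflect this, so the test runs below its nominal level and may give up the precision that matching was meant to buy. This is so whether matching is individual or by frequency.

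The OR is affected differently. In a matched case-control design, leaving out matching factors that are related to the exposure pulls the exposure OR toward 1. Its confidence interval can then miss the sex- and age-adjusted value too often. Because no covariates are named, the model could also be settled after the data are seen.

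Two smaller points follow. The age gap of up to 5 years within a match is left unadjusted. And if sex or age is reported among the risk factors, its OR cannot be interpreted, because the design fixed it.

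**Working it through.** **Inputs from the documents** (Study Design and Patient Selection): two-sided alpha 0.05, power 0.80, difference 0.65 SD, at least 39 per group, 40 patients anticipated, 1:1 matching on sex and age within 5 years, and an expected 1:1 sex ratio.

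**Assumed:** r, the share of angle variance explained by sex and age. The documents give no value, so 0, 0.1, 0.2 and 0.3 are shown.

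**1. The plan's sample size.** The normal approximation gives n = 2 × ((1.960 + 0.842)/0.65)² = 37.15, rounded up to 38. The noncentral t calculation gives 38.14, rounded up to 39, which is the stated figure. The sizing therefore also treats the groups as unmatched. With 40 per group, power is 0.819.

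**2. The t test, by formula.** Take the within-group SD as 1.
- The two-sample test uses SE = √(2/40) = 0.2236. Under matching the true SE is about √(2(1−r)/40), so the overstatement is about 1/√(1−r). At r = 0.2 this is 1/√0.8 = 1.118.
- Type I error is about 2 × (1 − Φ(1.96/√(1−r))), which is 0.050 / 0.039 / 0.028 / 0.019.
- A paired t test has standardised effect 0.65/√(2(1−r)), giving power 0.81 / 0.85 / 0.89 / 0.92 with 40 pairs.

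**3. The OR, by formula.** With normal angles of equal variance, the log-OR per SD is 0.65 without sex and age, and 0.65/(1−r) given them. The first gives exp(0.65) = 1.92 at every r. The second gives exp(0.65) = 1.92, exp(0.722) = 2.06, exp(0.8125) = 2.25 and exp(0.929) = 2.53.

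**4. Simulation with the age caliper.** 40 matched sets, 20 men and 20 women per group. Assumed: patient ages uniform over 50–80, control age within ±5 years and at least 50, sex and age each explaining half of r. There were 50,000 data sets per setting for the tests, 200,000 pairs for the large-sample ORs and 5,000 data sets for coverage.

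| r | 0 | 0.1 | 0.2 | 0.3 |
|---|---|---|---|---|
| Two-sample SE too large by | 0% | 5% | 12% | 19% |
| Type I error, two-sample t | 5.0% | 4.0% | 2.9% | 2.0% |
| Type I error, linear model (group, sex, age) | 5.0% | 5.0% | 5.0% | 5.1% |
| Power, two-sample t | 0.82 | 0.83 | 0.84 | 0.85 |
| Power, paired t | 0.81 | 0.85 | 0.88 | 0.92 |
| Power, linear model | 0.82 | 0.86 | 0.89 | 0.93 |
| OR per SD without sex and age | 1.92 | 1.92 | 1.91 | 1.89 |
| OR per SD with sex and age | 1.92 | 2.07 | 2.26 | 2.51 |
| Coverage of adjusted OR, unadjusted 95% CI | 95% | 95% | 92% | 80% |
| Coverage of adjusted OR, adjusted 95% CI | 95% | 95% | 96% | 95% |

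For example, the SE overstatement at r = 0.2 is 0.2236/0.2003 = 1.12. The mean difference at a true 0.65 SD averaged 0.647–0.649, so it is essentially unbiased.

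**5. Sensitivity to the age assumption.** With ages roughly normal around 63 (SD 8, none below 50), type I error of the two-sample t test was 5.1 / 3.9 / 2.8 / 1.9%. The ORs were 1.92 / 1.90 / 1.90 / 1.90 without sex and age and 1.92 / 2.05 / 2.25 / 2.55 with them. The picture is the same.

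**6. The age subgroups.** Each group is split by age separately, so members of a pair can fall on different sides. With patient ages spread over 20 / 25 / 30 years, a median split breaks on average 5.2 / 4.2 / 3.6 of 40 pairs, and at least one pair in 99 / 97 / 94% of studies.

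**The case against.** The strongest reply is that nothing in the documents shows the angles to depend on sex or age. At r = 0 there is no effect, and at r = 0.1 it is small: type I error 4.0% instead of 5.0%, power 0.83 against 0.86, OR coverage 95% either way. The 80% coverage figure needs r = 0.3. All of this stands, and it is why the point is conditional.

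Second, the t test remains valid. Its error is on the conservative side, power stays above the planned 0.80 at every r, and the test agrees with the sample size calculation. This also stands: for the angles the loss is precision, not validity.

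Third, the plan does not say that sex and age will be left out of the logistic model. True, but it does not say they will be included, and that gap is itself a reason to name them.

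Fourth, adjustment does not make the OR estimate more accurate at this size. Measured against the adjusted log-OR, root mean squared error at r = 0 / 0.1 / 0.2 / 0.3 is 0.27 / 0.26 / 0.28 / 0.34 unadjusted and 0.28 / 0.30 / 0.32 / 0.35 adjusted. This stands. What adjustment buys is correct coverage, and that matters from about r = 0.2.

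Finally, the sex and age subgroups and the comparison of demographics use these factors in part, but neither adjusts the main comparison.

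**Conclusion.** The concern holds. The design matches on sex and age, and no stated between-group analysis uses the matching or adjusts for it. If sex and age explain 10–30% of angle variance, the two-sample t test has a true type I error of 4.0–2.0% and forgoes about 3 to 8 percentage points of power (0.83–0.85 against 0.86–0.93). An OR per SD from a model without them is about 1.9 instead of 2.07–2.51. If they explain none, nothing is lost.

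These sizes rest on the assumed r, 40 complete pairs, normally distributed angles and the assumed age distribution. There is no added false-positive risk and the planned sample size is not made inadequate. The plan should still be changed, because these are the study's main results and the better analysis costs almost nothing.

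**What to change.** 1. Analyse FIA and TIA with a linear model containing group, sex and continuous age, overall and in the subgroups (dropping sex within a sex subgroup). It is valid under individual or frequency matching and deals with the residual age gap.
2. Always include sex and continuous age in the logistic model for the ORs, including any model with joint type as the factor. Keep the χ² and Mann-Whitney tests as unadjusted descriptions.
3. State whether matching is individual. If it is, record a pair identifier and add the paired t test, McNemar's test and conditional logistic regression as sensitivity analyses on the full sample only, since the age split will usually break some pairs.
4. Do not interpret ORs for sex or age as risk-factor estimates.

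**Cost.** SAP wording, plus a pair identifier if matching is individual; sex and age are already needed for the matching. At r = 0 the linear model has power 0.816 against 0.817 for the two-sample t test, and the paired t test 0.807. With 40 pairs, adjusted and conditional log-ORs both run about 6–9% too high on average. The conditional ones are also noisier (root mean squared error 0.31 / 0.35 / 0.37 / 0.40 at r = 0 / 0.1 / 0.2 / 0.3), so they should serve as sensitivity analyses only. All ORs should be read with their confidence intervals.

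### The old/older age split is made separately in patients and controls and by count, so the two groups can be divided at different ages

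*Combined protocol and SAP*

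**What the plan says.** Under Study Design and Patient Selection, 40 patients aged 50 or over are enrolled first. Controls follow, one per patient, "matched for sex and age (within 5 years) to the patients". No mean, spread or upper limit of age is given.

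Under Statistical Analysis Plan, "the participants of each group will be separately grouped into sex subgroups and into two age subgroups". The rule for age is a count: "The old age subgroup of each group will include approximately 20 participants with earlier ages", the remainder form the older subgroup, and "The number of participants in each subgroup will be as close as possible to 20". Patients and controls are then compared on FIA and TIA within each subgroup: "The two-sample t tests will be repeated for each sex subgroup and age subgroup in isolation".

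No common age in years is stated, nothing keeps a matched pair on the same side of the split, and the plan does not ask for the dividing ages to be reported.

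**The concern.** An age-subgroup result is a statement about people in an age range. Here the range is set by ranking patients among patients and controls among controls, so the label depends on case status as well as on age. With matching only to within 5 years, the two rankings need not break at the same age. A 63-year-old patient could be *old* and a 63-year-old control *older*.

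At stake is what the four age-subgroup comparisons (FIA and TIA, in each of two subgroups) refer to. If the dividing ages differ, patients and controls are compared over slightly different age ranges, and the report has no single range to attach to the result. The main FIA and TIA comparison and the sex subgroups do not use this split.

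**Working it through.** **The plan's own figure.** The documents give no number for the dividing age. The nearest figure is the sample size: "a minimum of 39 subjects per group was needed" at a two-sided 5% level and 80% power, with an "assumed mean difference between two groups=65% of the standard deviation". The noncentral t distribution gives power 0.799 at 38 per group and 0.809 at 39, so 39 is reproduced.

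**Upper limit of the gap.** Let P be the age of the 20th youngest patient and C that of the 20th youngest control. At least 20 patients are aged P or less. Their matched controls are aged P + 5 or less, so C ≤ P + 5. The same argument with the groups exchanged gives P ≤ C + 5. Hence |P − C| ≤ 5 years if every pair meets the tolerance and both groups split 20/20.

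**Typical gap (simulation; the inputs below are assumptions).** 20,000 simulated studies per scenario, 40 pairs, whole-year ages, everyone 50 or over. Patient ages were uniform 50–80, uniform 50–70, or normal (mean 62, SD 7) truncated at 50. Control-minus-patient differences were spread evenly over ±5 years. The plan does not say how the cut is placed between ages, so three readings were tried. Results are in the order of the three age distributions.

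| Placement of the cut in each group | Mean gap, years | Gap ≥ 1 year | Gap ≥ 2 years |
|---|---|---|---|
| 20th ordered age | 1.11 / 0.92 / 0.86 | 73 / 68 / 65% | 29 / 21 / 18% |
| Midpoint of 20th and 21st | 1.04 / 0.90 / 0.84 | 58 / 52 / 50% | 19 / 13 / 10% |
| Whole-year cut nearest 20, equal ages together | 1.08 / 0.87 / 0.81 | 72 / 66 / 64% | 28 / 18 / 16% |

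In the first and third rows one year is the smallest non-zero gap, so the middle column there is the chance that the two dividing ages differ at all. Under the third reading, some patient and control of equal age are labelled differently in 51 / 56 / 56% of studies.

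Closer matching shrinks the gap. With differences spread over ±2 years the mean (20th ordered age) is 0.69 / 0.59 / 0.54. A separate calculation over a wider set of age distributions gave 0.54–0.77 when differences cluster near zero within ±5 (triangular) and 0.46–0.61 when they are uniform over ±2.5. The range over symmetric models is therefore about 0.5 to 1.1 years.

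**Age balance within subgroups.** The measure is the average absolute difference in mean age between patients and controls in an age subgroup. To compare like with like, equal ages are kept together under both rules.

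| Assumed matching | Separate cuts | One pooled cut |
|---|---|---|
| Symmetric ±5 | 0.66 / 0.68 / 0.72 years | 0.73 / 0.68 / 0.71 years |
| Controls all 0–5 years younger | 2.1–2.3 years | 0.9–1.0 years |

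Under symmetric matching the pooled cut is 0.07 worse, equal, and 0.01 better. It also splits no fewer matched pairs: 4.0 / 5.7 / 6.5 of 40, against 3.8 / 5.5 / 6.4 with separate splits. It relabels 1.4 / 1.7 / 1.9 of 80 participants on average. In the second row, which is a sensitivity case and is not in the documents, the mean gap between separate cuts is about 2.5 years. The pooled cut then splits more pairs (3.7–6.1 against 2.2–3.7).

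**Price in cell size and power.** With the pooled cut the smallest of the four cells averages 18.8 / 18.5 / 18.3 under symmetric matching and 17.7 / 16.8 / 16.2 if controls run younger. For a 0.65 SD difference at 20 v 20, the noncentrality is 0.65 × √(20 × 20 / 40) = 2.06 on 38 degrees of freedom, and power is 51.7%. At 18 v 22 it is 51.3%, and at 16 v 24 it is 50.1%. The largest loss shown is 51.7 − 50.1 = 1.6 points.

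**The case against.** **The wording is not watertight.** The word *separately* could mean only that sex and age are two uncrossed groupings, and the target of 20 is approximate. One common cut would often leave all cells near enough to 20 to comply. This stands as far as it goes, but the rule defines the younger subgroup of each group by a count in that group, which favours a cut per group. On either reading no common age is stated.

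**The fix buys no age balance in the base case.** Correct. Under symmetric matching the two rules are practically equal. A reader might infer that a common cut-off reduces confounding by age here; the calculation does not support that.

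**The effect on the angles may be negligible.** The documents give no relation between age and FIA or TIA. Suppose, purely for illustration, a trend of 0.3 SD per decade. An imbalance of 0.65 years then shifts a subgroup difference by 0.65 × 0.03 ≈ 0.02 SD, against a standard error of √(2/20) ≈ 0.32 SD. A reader might infer that the age-subgroup t tests are invalid or materially biased; nothing in the plan shows that.

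**A systematic age shift would be seen anyway.** The plan compares demographics between the groups, which can reveal an overall shift. It would not show the dividing ages or the imbalance within subgroups.

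**Conclusion.** The point holds as a matter of interpretation, at the level of something to consider. The plan sets the dividing age by count within each group while matching tolerates 5 years, so *old* and *older* can cover different ages in patients and controls. This follows from the text and needs no assumption.

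The size does rest on assumptions. The 5-year limit needs every pair within tolerance and 20/20 splits. The average of about 0.5 to 1.1 years needs an assumed age distribution and symmetric matching. A reader might take 1 year, or even 5, as the expected discrepancy. One year is towards the upper end of the symmetric range and arises when the full ±5 window is used evenly; 5 years is only a limit. An average gap of about 2.5 years requires controls to run 0–5 years younger throughout, which the documents do not suggest.

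The t tests remain valid, and the overall and sex-subgroup comparisons are untouched.

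**What to change.** Replace the per-group count with one rule: both age subgroups are defined by a single cut-off in whole years applied to patients and controls alike, for example the median age of all participants pooled, fixed without reference to FIA or TIA. Keep participants of equal age together. Report the cut-off and, by group, the age range of each subgroup.

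This is one sentence in the Statistical Analysis Plan. The gain is one interpretable age range per subgroup, plus protection of age balance if controls turn out systematically younger or older than their patients. The cost is that cells will not be exactly 20: the smallest averages about 18–19 under symmetric matching and about 16–18 if controls run younger, with at most about 2 points less power per subgroup. The pooled median is known only once controls are enrolled, so the plan should fix the rule for finding the cut-off now, not its value.

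If the separate split is preferred for its equal cells, the minimum is to report both dividing ages and how tied ages were assigned.

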Standing anteroposterior knee radiographs and special PTFJ radiographs will be taken for the participants in both groups. The standing anteroposterior knee radiographs will be obtained with the knee extended. The PTFJ radiographs will be acquired with the knee of the participants in approximately 45°-60° of internal rotation. In this projection, the PTFJ articulation can be clearly visible.

Radiographic Evaluations and Measurements

For the standing anteroposterior knee radiographs, radiographic knee osteoarthritis will be evaluated by using the Ahlbäck grading scale, and the femorotibial angle (FTA) will be measured. For the PTFJ radiographs, the degenerative joint disease of the PTFJ will be staged with the Kellgren-Lawrence staging system, and the fibular inclination angle (FIA) and the tibial inclination angle (TIA) of the PTFJ surface to the longitudinal axis of both fibula and tibia will be measured separately. The horizontal type of PTFJ will be defined as the inclination

angle $\leq 20^\circ$, and the oblique type will be defined as the inclination angle $> 20^\circ$.

Radiograph annotations will be deleted. Each participant will be assigned a random and unique number, and participants of the two groups will be mixed. All radiographic evaluations and measurements will be carried out in a blinded, independent, and random fashion by a radiologist, who do not know the study hypothesis, with tools of the digitized picture archiving communication system (PACS, RADinfo Technologies Co.,Ltd, Hangzhou, China). Additionally, 20 participants per group will be randomly selected. The FIA and TIA of the 40participants will be measured again after 1 month by the same radiologist and an orthopedic surgeon who do not know the study hypothesis. The intraobserver reliability and interobserver reliability in the FIA and TIA measurement will be assessed by using an intraclass correlation coefficient (ICC).

Statistical Analysis Plan

Statistical analysis will be performed with SPSS (v25.0; IBM Corp). $P < .05$ will be considered significant. Demographics, laterality of included knees and FTA will be compared between the patient and control groups by using two-sample t test or χ^2 test. Paired-samples t test will be used to compare the difference between the FIA and TIA of all participants.

Any differences of the FIA and TIA between the patient and control groups will

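### The sex and age subgroup t tests come without an interaction test, so their separate P values cannot show whether the association differs by sex or age

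*Combined protocol and SAP*

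**What the plan says.** Study Design and Patient Selection gives a single objective: "The study will be performed to compare the inclination angle of the PTFJ surface in participants with and without medial compartment knee osteoarthritis". The sample size calculation covers that overall comparison only. It uses two-sided alpha 0.05, 80% power and "an assumed mean difference between two groups=65% of the standard deviation", and arrives at 39 per group.

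The Statistical Analysis Plan compares FIA and TIA between patients and controls by two-sample t test. It then splits each group by sex and into two age halves, and states: "The two-sample t tests will be repeated for each sex subgroup and age subgroup in isolation".

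Subgroup sizes come from two places:
- **Age halves:** "The number of participants in each subgroup will be as close as possible to 20".
- **Sex:** the size follows from "The anticipated number of patients is 40, and the female-to-male ratio is expected to be 1:1" together with controls matched 1:1 on sex.

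One significance threshold, P < .05, applies to all tests. The only regression is described as follows: "The odds ratios (ORs) for risk factors of medial compartment knee osteoarthritis will also be calculated by using binary logistic regression analysis". It lists no covariates and no interaction terms.

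**The concern.** Whether an association differs between men and women is a question about the difference between two differences. Two separate P values do not estimate that quantity. With about 20 per group in each stratum, one test can cross .05 and the other miss it by chance alone, even when the true patient-control difference is identical in both.

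The plan supplies neither the test that would answer the question nor a caution against answering it from the separate tests. If the report reads a significant result in one stratum and a non-significant one in the other as a sex- or age-specific association, that conclusion would have no support. The plan does not say it will do this. The misreading is a risk left open, not a stated rule.

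**Working it through.** **Inputs from the documents.** Effect 0.65 SD; two-sided alpha 0.05; power 0.80; 39 per group required; 40 patients anticipated, half of them women; controls 1:1, matched on sex and on age within 5 years; about 20 per group in each subgroup; threshold P < .05; two angles and four subgroups.

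**Assumptions.** The SD is the same in all subgroups. The groups are treated as independent, as the planned two-sample tests treat them. The documents give no FIA-TIA correlation, so a range of 0 to 0.95 is used. For the simulations, patient ages are taken as uniform from 50 to 80.

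**1. The plan's own figure.** By the noncentral t distribution, 39 per group at 0.65 SD gives 80.9% power and 38 gives 79.9%. The stated 39 reproduces.

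**2. Number of tests.** 2 angles × 4 subgroups = 8.

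**3. Power of one subgroup test.** With 20 per group at 0.65 SD, power is 51.7%. Reaching 80% would need an effect of 0.909 SD.

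**4. Discordant results when the effect is uniform.** The two levels of a factor contain different participants. With power p in each, the chance that exactly one is significant is 2p(1 − p). At 0.65 SD this is 2 × 0.517 × 0.483 = 0.499. For other uniform effects:

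| True effect, same in both levels | Exactly one level significant |
|---|---|
| 0.4 SD | 36% |
| 0.5 SD | 45% |
| 0.65 SD | 50% |
| 0.8 SD | 43% |
| 1.0 SD | 23% |
| 1.2 SD | 8% |

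Simulating the planned layout (40 per group, 20 per sex, age split 20/20 within each group) at 0.65 SD gives 49.5-50.3% for sex and 49.7-50.2% for age.

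**5. At least one significant result with no effect anywhere.** Eight independent tests would give 1 − 0.95^8 = 34%. The sex and age subgroups overlap and the two angles may be correlated, so the simulated rate is lower: 30.1%, 27.5%, 23.9%, 21.7% and 20.2% at correlations of 0, 0.5, 0.8, 0.9 and 0.95.

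**6. What an interaction test can do here.** With four cells of 20, the difference of two differences has SE = √(4/20) = 0.447 SD, on 76 degrees of freedom.
- Power for a 0.65 SD difference in effect: 30.0%.
- Difference detectable with 80% power: about 1.27 SD.
- Cell size for 80% power at 0.65 SD: 4 × [(1.96 + 0.84)/0.65]² ≈ 74.3, so 75 per cell.
- 95% CI half-width: about 1.99 × 0.447 = 0.89 SD.

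In a joint model with both interactions (74 degrees of freedom), simulation gives 29% power for sex at 0.65 SD. For the age halves it gives 28-29%, depending on whether the effect changes linearly or as a step at the median. Each interaction test rejects about 5% of the time when effects are uniform (4.5-5.6% across settings).

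**The case against.** The strongest reply is that the plan announces no inference about sex or age. Its one objective is the overall comparison, and repeating a test within strata can serve as a consistency check. That is fair, and it is why the harm is conditional. But the consistency reading is not stated either, and tests with about 52% power are a poor check of consistency; estimates with confidence intervals would do that better.

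The 50% figure also sits at the mathematical maximum of 2p(1 − p). This stands. It is the chance of discordant P values, falls to 8% at 1.2 SD, and becomes a rate of false claims only if discordance is read as effect modification.

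The 20-30% figure is a multiplicity point, separate from the interaction point. This also stands. Four unadjusted interaction tests would still carry about a 12-19% chance of at least one false positive, at correlations from 0.95 to 0. The exploratory label deals with that; the model does not.

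The interaction test has low power. That is true, but it favours showing the estimate and its wide interval, because separate P values hide how little 80 participants can say on the question.

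Finally, the age halves are cut within each group, so some matched pairs fall in different halves: about 3-4 of 40 if ages are uniform from 50 to 80 and control ages are uniform within 5 years of the patient's. The simulated error rates hold with the halves cut in this way.

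**Conclusion.** The concern holds, for these subgroup analyses only. As planned, the 8 tests cannot show whether the association differs by sex or age, and nothing in the plan stops them being read as if they could. At the plan's assumed 0.65 SD, if uniform, discordance between the two levels of a factor is close to a coin toss for each angle. The closed-form figures rest on 20 per group, equal SDs and independent groups. The 20-30% null rate also rests on the assumed correlation and age distribution.

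The point should be addressed, but it does not threaten the main result: the overall FIA and TIA comparison and its sample size stand.

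**What to change.** For each angle, fit one linear model to all participants with group, sex, age half, group × sex and group × age half. This keeps the plan's own subgroups. If continuous age is preferred, report the group × age interaction as a slope.

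Add to the Statistical Analysis Plan:
- Any statement that the association differs by sex or age will rest on the interaction estimate and its 95% CI.
- Subgroup mean differences will be reported with 95% CIs and labelled exploratory and descriptive.
- A non-significant interaction will not be taken to show equal effects.

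**Cost.** A few lines of text and one model per angle, on data the study already collects. The drawback is precision: intervals of about ±0.9 SD, so the likely finding is inconclusive.

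The power figures for the age halves do not carry over to continuous age, where power depends on the age spread and the shape of the effect. With ages assumed uniform from 50 to 80, it is about 22-24% for a 0.65 SD step at the median and about 37% for a linear 0.65 SD change over 15 years.
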